Gut Microbiomes and Viromes in Patients with Metabolic Syndrome

NCT number:

Date: 7 November 2017

Background

Metabolic syndrome (MS) is an umbrella term that describes conditions such as high blood pressure, elevated blood concentrations of triglycerides, cholesterol and sugar, and excess deposition of body fat. Individuals afflicted with one or more of these MS components are predisposed to obesity, diabetes and various heart-related diseases compared to persons without such conditions.

There is mounting evidence that the human gut microbiome plays a vital role in health and wellbeing. In particular, human population association and mouse model studies have demonstrated that gut microorganisms can be reproducibly linked to diseases such as obesity and diabetes. There is, however, considerably less effort directed towards applying these notable findings to healthcare of the general public, which is complicated by the fact that gut microbiomes are heavily influenced by biogeography, ethnicity, lifestyle and diet.

Objective

To assess variation in the gut microbiomes of healthy and MS individuals specific to Hong Kong, and to explore gut microorganisms as predictive/diagnostic markers of MS and clinical outcomes associated with medical interventions.

Primary Objectives

1. Generate a reference healthy gut microbiome database representative of the general adult population in Hong Kong
2. Describe how the gut microbiomes of individuals with MS deviate from the healthy reference

Secondary Objectives

1. Assess viability of using gut microbiome as clinical markers for disease prediction and progression
2. Characterise changes in gut microbiome in response to medical treatment, supplementation with probiotics/prebiotics, changes to lifestyle and other interventions

Research Plan and Methodology

The proposed project will have two phases: (1) *Phase 1* - A cross-sectional gut microbiome survey in healthy and individuals suspected to have MS to assess variation between 'healthy' and 'diseased' gut microbial communities, followed by (2) *Phase 2* - A longitudinal observational study of MS and partial MS patients undergoing clinical monitoring or treatment according to the current practice of the Lek Yuen Health Centre to describe changes in the gut microbiome associated with drug intake, lifestyle modification, probiotics/prebiotics intake and other interventions.

(1) Phase 1: Cross-sectional survey

Study population: Potential study subjects will be invited from health talks, blogs, notices and advertisement through various public media channels, as well as patients referred to the Lek Yuen Health Centre for suspected or confirmed MS. They will be classified into three groups: (i) Metabolic Syndrome-Full, (ii) Metabolic Syndrome-Partial, and (iii) Controls (Non-Metabolic Syndrome) according to criteria modified from the International Diabetes Foundation:

1. Waist circumference ≥ 90 cm (M), ≥ 80 cm (F)
2. Blood pressure: $\geq 130/85$ mm Hg
3. Triglycerides: ≥ 1.7 mmol/L
4. High-density lipoprotein cholesterol: < 1.03 mmol/L (M), < 1.29 mmol/L (F)
5. Fasting blood sugar: ≥ 5.6 mmol/L

- (i) Metabolic Syndrome-Full: any three or more of the five criteria
- (ii) Metabolic Syndrome-Partial: any one or two of the five criteria
- (iii) Controls (Non-Metabolic Syndrome): none of the five criteria

Exclusion criteria

1. Age: <35 or >65 years
2. Major organ system impairment: such as heart failure, renal failure, and severe impairment of respiratory function.
3. On long-term regular immunosuppressive therapy.
4. Current or history of malignancy.
5. Current or history of major gastrointestinal diseases, including inflammatory bowel disease, major gastrointestinal surgery, malignancy.
6. Current medication for glucose or lipid control, such as metformin and statin.

Sample size:

Using published gut microbiome and clinical data collected from a Swedish cohort (Karlsson et al. Nature 498.7452 (2013): 99), we estimated that 731 subjects allowed for 80% power in detecting a 1% difference in gut microbiome community diversity at 95% confidence between individuals with no or one of the above MS conditions other than blood pressure. Since we are proposing an observational study and gut microbiomes are highly variable even within cohorts, we aim to collect more than the estimated number of samples, detailed below:

1. Metabolic Syndrome-Full: 500 (male:female = 1:1)
2. Metabolic Syndrome-Partial: 500 (male:female = 1:1)
3. Controls (Non-Metabolic Syndrome): 500 (male:female = 1:1)

The second phase of the study will involve participants from the full and partial metabolic syndrome cohorts, hence we expect to survey around 1000 subjects. Based on the above estimate of 731 subjects for 80% power, we expect that 1000 subjects will still be sufficient to detect differences in microbial community diversity between the cohorts in part 2 of this study.

Clinical data & specimen collection:

At enrolment:

- Patients will be asked to complete a questionnaire to record demographic information such as age, gender, diet, lifestyle, socioeconomic status, history of illnesses and medication use
- A series of measurements will be recorded from the study subjects, including waist circumference, blood pressure, height and weight.
- A stool sample will be collected for studying the gut microbiome.
- 10 ml of blood sample will be collected for sugar, triglycerides, cholesterol and lipid measurements.

- 10 ml of blood sample will be stored for future studies of metabolic profiles and host genetics.

(2) Phase 2: Longitudinal observational study

Study population:

Subjects from Phase 1 of the study recommended to undergo medical follow-up at the Lek Yuen Health Centre will be invited to participate in Phase 2 “Longitudinal observational study”. These subjects will either be Metabolic Syndrome-Full or Metabolic Syndrome-Partial. This study will not involve any changes to the subjects’ medical procedures- any drug prescriptions and/or intervention will be according to the examining doctor’s discretion and we will only monitor changes in the gut microbiome composition associated with these clinical procedures.

At follow-up visits:

- Subjects belonging to the “Metabolic Syndrome-Full (N = 500)” and “Metabolic Syndrome-Partial (N = 500)” cohorts will be re-examined at regular intervals according to the current practice of the clinic which depends on the need for drug treatment. Patients started on new medication are usually followed-up at 4-6 weeks, those on regular medication at 3-6 months.
- For the purpose of this study, each subject will be followed up to 36 months.
- At each follow-up visit, detailed clinical history, medication and lifestyle changes will be recorded. The 5 parameters for metabolic syndrome will be reassessed at each follow-up visit.
- 10 ml of fasting blood will be collected for glucose, triglycerides, cholesterol, and lipid measurements.
- A stool sample will be collected for studying changes in the gut microbiome.
- A urine sample will be collected for measuring excreted concentrations of any medication consumed
- Depending on subjects’ follow-up frequency, each subject will be providing a total of six to nine blood, urine and stool samples over the 36-month duration of this study.

Gut microbial community data generation and analyses:

The collected stool samples will be used for investigating the gut microbial community composition using small subunit 16S ribosomal RNA gene amplicon and bulk DNA shotgun sequencing. 16S amplicons will be PCR-amplified from extracted stool DNA and then sequenced to create microbial community profiles. In addition, metagenome sequencing will be performed to identify the genomic potential of the gut microbiome in a subset of samples chosen based on results

of the 16S microbial community profiles, demographic information and clinical measurements. These results will be correlated with answers provided in the questionnaire and clinical measurements to identify associations between the gut microbiome and health status of the study subjects.

Patient Confidentiality

All information collected in the study will be kept confidential. Patient data will be coded with specifically assigned sample numbers and kept free of personal identifiers. All digital copies will be stored on an encrypted hard drive.

Ethical Considerations

This is an observational study where patient management including all pharmaceutical and non-pharmaceutical interventions will be conducted according to the current practice of the Lek Yuen Health Centre. The stool collection procedures are non-invasive, and should not create pain or discomfort. Blood samples will be collected from participants, and could result in a small degree of pain or bruising. This will be minimised by assigning experienced staff to draw blood samples.

Ethics Compliance

All study procedures will be carried out in compliance with the Declaration of Helsinki.

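### Primary objective 1 promises a healthy reference for Hong Kong's general adult population, but the protocol admits nobody under 35 or over 65

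*Protocol*

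**What the plan says.** Primary Objectives, item 1 of the protocol is to "Generate a reference healthy gut microbiome database representative of the general adult population in Hong Kong". It states no age limits.

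Under Phase 1, Exclusion criteria, item 1 reads "Age: <35 or >65 years". The exclusions are listed once, after the three study groups have been defined, and no group is exempt. The Sample size section plans "Controls (Non-Metabolic Syndrome): 500 (male:female = 1:1"; this group meets none of the five metabolic criteria and so provides the healthy reference.

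On recruitment, the Study population section says: "Potential study subjects will be invited from health talks, blogs, notices and advertisement through various public media channels". The other source is "patients referred to the Lek Yuen Health Centre for suspected or confirmed MS".

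The Background notes that too little has been done towards "applying these notable findings to healthcare of the general public" and that "gut microbiomes are heavily influenced by biogeography, ethnicity, lifestyle and diet". Secondary Objectives, item 1 is to "Assess viability of using gut microbiome as clinical markers for disease prediction and progression".

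**The concern.** The objective names one population and the eligibility criteria admit a narrower one. Adults under 35 and over 65 belong to the stated target but have no chance of entering the reference.

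The word healthy in the objective accounts for the disease and medication exclusions and for the rule that Controls meet none of the five criteria. Those are not at issue. It does not account for an age cut, because there are healthy adults on both sides of it.

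What is at stake is the scope of a primary deliverable. The wording of objective 1 sets what the study may conclude and how others may use the database. As written, it could be offered as a healthy benchmark for ages on which it holds no data. The protocol's interest in public healthcare and in clinical markers makes that use foreseeable.

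**Working it through.** This is a consistency check of stated target against stated eligibility. The protocol attaches no figure to the point that could be reproduced; its sample size of 731 is not an input.

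**Step 1: target and eligibility side by side**

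| Element | Protocol section | Content |
|---|---|---|
| Target of the reference | Primary Objectives, item 1 | Adults of Hong Kong in general, no age limit |
| Ages admitted | Exclusion criteria, item 1 | 35 to 65 inclusive |
| Who supplies the reference | Study population; Sample size | 500 Controls, 250 of each sex |

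Nothing elsewhere in the protocol narrows the meaning of adult to 35–65, exempts Controls from the age rule, or plans a second sample for other ages. So 0 of the 500 Controls can lie outside 35–65.

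**Step 2: can the analysis close the gap?**

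No. Weighting scales each sampled person by the inverse of the probability of selection. For ages under 35 or over 65 that probability is zero, so there is nobody to weight. This is therefore not something a statistical analysis plan could supply.

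**Step 3: how much of the adult age range is covered**

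Ages covered: 65 − 35 + 1 = 31. The protocol does not define adult. If adulthood starts at 18, the ages 18 to 34 (34 − 18 + 1 = 17) and every age from 66 up are absent. Share of single-year ages, under assumed start and end ages:

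| Assumed adult range | Number of ages | Share covered |
|---|---|---|
| 18–80 | 63 | 31/63 = 49% |
| 18–90 | 73 | 31/73 = 42% |
| 21–80 | 60 | 31/60 = 52% |
| 21–90 | 70 | 31/70 = 44% |

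Ending the range at 75 instead would raise the top figure to 31/55 = 56%. These are shares of ages, not of people. The protocol does not give the Hong Kong age distribution.

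**Step 4: representativeness within 35–65**

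Recruitment is by open invitation and by referral to one health centre, with no sampling frame described, and the sex ratio is fixed at 1:1. Since the protocol itself names lifestyle and diet as strong influences on the microbiome, who comes forward may matter. This leaves representativeness within the age band unsupported, not impossible. The conclusion does not depend on it.

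**Step 5: effect on the other primary objective**

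Primary objective 2 compares subjects with metabolic syndrome against the reference. All three groups have the same age limits, so that comparison within 35–65 does not depend on the wording of objective 1.

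**The case against.** The best defence is that this is loose wording in a summary aim. The overall objective stresses findings specific to Hong Kong, so objective 1 may be meant as a claim about place, bounded by the eligibility rules that follow in the same short document. The age range is stated openly. No planned comparison, sample size or Phase 2 procedure changes. The Background does not list age among the strong influences on the microbiome, so the protocol itself does not show that a reference for other ages would differ. Misuse of the database outside 35–65 is a possibility, not a plan.

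Much of this stands. The practical consequence cannot be sized from the protocol, objective 2 is unaffected, and the recruitment argument is only supporting. The remark about public healthcare describes a gap in the field and is not a scope claim for this database.

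None of it removes the mismatch. The objective claims representativeness of adults in general, not merely a local origin, and the reader of a published reference will rely on that claim. Silence about age effects is no evidence that there are none.

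**Conclusion.** The point holds. Objective 1 as worded cannot be met by the design: the reference will contain no one under 35 or over 65, and no analysis can change that. The contradiction rests on the protocol's text alone. The coverage figure of 42% to 52% rests on the assumed limits of adulthood (start at 18 or 21, end at 80 or 90) and is a guide to scale only. How far the reference would be wrong for the missing ages, or through self-selection within 35–65, is unknown.

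This should be corrected because it governs what a primary deliverable may claim. It is a fault of stated scope and does not threaten the comparison between groups.

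**What to change.** Restate primary objective 1 as a reference for recruited Hong Kong adults aged 35 to 65 who meet none of the five criteria and satisfy the other eligibility rules. This is the essential change.

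Two additions would help users:

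- State the recruitment route and the 1:1 sex quota with the database.
- Report the reference by age and sex, both already recorded in the enrolment questionnaire, so that the ages covered are plain. The choice of age bands can be left to the statistical analysis plan.

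The cost is wording and descriptive reporting only. Recruitment, sample size and data collection do not change. The claim becomes narrower, and results by stratum are less precise. For the same SD, the width of an interval for a mean relative to that for all 500 Controls is √(500/n). One sex (n = 250) gives √2 = 1.41 times the width. Three equally filled age bands per sex, taken as an example (n = 500/6, about 83), give √6 = 2.45 times.

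### Treated hypertensives with a normal reading are neither excluded nor counted as having raised blood pressure, so some enter the healthy Controls

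*Protocol*

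**What the plan says.** The protocol's Phase 1 study population section sets five criteria. The second is "Blood pressure: $\geq 130/85$ mm Hg", with no clause on treatment or earlier diagnosis. Groups depend only on how many criteria are met: "Metabolic Syndrome-Full: any three or more of the five criteria", one or two for Partial, and "Controls (Non-Metabolic Syndrome): none of the five criteria".

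Two exclusion criteria concern current drugs. Item 3 covers long-term immunosuppressants. Item 6 reads "Current medication for glucose or lipid control, such as metformin and statin", and no reason is given for it. Neither names blood-pressure drugs. Item 2, on major organ impairment, would remove only those hypertensives who also have such impairment.

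The enrolment questionnaire records "socioeconomic status, history of illnesses and medication use". The section on microbial data generation and analyses correlates sequencing results with the questionnaire answers. Neither section uses these data to assign the group.

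The Background describes metabolic syndrome as covering "conditions such as high blood pressure, elevated blood concentrations of triglycerides, cholesterol and sugar" and excess body fat. Primary Objective 1 is to "Generate a reference healthy gut microbiome database representative of the general adult population in Hong Kong". Primary Objective 2 describes how people with metabolic syndrome depart from that reference.

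**The concern.** The protocol does not handle drug treatment evenly across the components. For glucose and lipids, current drug users are excluded, so a treated value cannot pass as a normal one. For blood pressure, treated people stay in and are grouped by the treated reading. A person with drug-controlled hypertension and no other criterion is then indistinguishable, by the grouping rule, from someone who never had raised blood pressure.

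The Control group is meant to be the healthy reference. Placing people in it who have one of the conditions named in the Background, and who take drugs for it, blurs what that reference represents. It also blurs the contrast described in Primary Objective 2. Such people also fall outside Phase 2, which is limited to Full and Partial subjects, although Phase 2 is intended to study microbiome change associated with drug intake.

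**Working it through.** **The plan's own figure.** The only effect size is in the sample size section: 731 subjects for 80% power to detect a 1% difference in diversity. It cannot be reproduced, because no standard deviation, mean diversity or group split is given. That comparison was also drawn "between individuals with no or one of the above MS conditions other than blood pressure", so it does not describe the blood-pressure component. Nothing below depends on it.

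**The grouping rule.** Let k be the number of the other four criteria met (0 to 4). The group is Control for a count of 0, Partial for 1 or 2, and Full for 3 or more. For a treated hypertensive reading below 130/85, the rule as written gives a count of k. Counting the component gives k + 1.

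| Other criteria met (k) | As written (count k) | Component counted (count k + 1) | Group changes? |
|---|---|---|---|
| 0 | Control | Partial | Yes |
| 1 | Partial | Partial | No |
| 2 | Partial | Full | Yes |
| 3 | Full | Full | No |
| 4 | Full | Full | No |

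The group changes at two of the five values of k. This is a property of the rule, not a share of subjects. Only k = 0 touches the healthy reference; at k = 2 only the Partial/Full label moves.

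**Could another provision catch these people?**
- Exclusions: items 2, 3 and 6 do not remove an otherwise eligible user of blood-pressure drugs.
- Enrolment data: the questionnaire could identify them, but the group definitions do not refer to it.
- Planned correlation with questionnaire answers: this can show drug use afterwards, but leaves the labels, the quota of 500 per group and the limit on Phase 2 as they are.

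**Screening cost of counting treatment.** The Control quota is 500 at a 1:1 sex ratio, so 500/2 = 250 per sex. Let q be the share on drugs for high blood pressure among people who meet no measured criterion. Filling the quota then takes 250/(1 − q) such people per sex. The protocol does not give q, so the values here are assumptions:
- q = 5%: 250/0.95 = 263.2, so 264 per sex
- q = 10%: 250/0.90 = 277.8, so 278 per sex
- q = 20%: 250/0.80 = 312.5, so 313 per sex

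**The case against.** The strongest reply is that grouping by measured status is a usable definition, and that this is a design choice rather than a contradiction. The protocol says its criteria are modified from an outside definition, and its sample size comparison leaves blood pressure aside. Item 6 gives no purpose, so it need not have been meant to stop drugs masking a component. This is fair as to intent. It does not change the effect: the modification is not described, and treated blood pressure is not addressed anywhere.

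A second reply is that the affected set may be small. To enter the Controls, a person must be treated, controlled below the threshold, and normal on waist, triglycerides, HDL cholesterol and glucose. This stands, and is why no size is claimed.

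A third is that the data allow regrouping later, and that a sensitivity analysis normally belongs in an SAP. The first part stands for analysis, but later regrouping cannot refill a quota or restore Phase 2 eligibility. The absence of a sensitivity analysis is not itself the criticism; the grouping rule is fixed in the protocol.

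A fourth is that Phase 2 invites those advised to have follow-up at the health centre, and nothing shows a treated Control would have been so advised. This also stands. The Control label rules such a person out, but it may not be the only thing that does.

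Finally, counting treatment places all use of these drugs in the MS groups, which brings its own confounding. That is a real cost and is dealt with under the fix.

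**Conclusion.** The concern holds. Followed exactly, the protocol classes a drug-controlled hypertensive with no other criterion as a healthy Control, and one with exactly two others as Partial rather than Full. The first case matters more, because it enters the reference used by both primary objectives. The second affects only the boundary between the two MS groups, and both remain eligible for Phase 2.

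The conclusion rests on the text of the criteria, group definitions and exclusions, and on the assumption that some such people enrol. That is plausible: recruitment covers ages 35 to 65, through public channels and through referrals for suspected or confirmed metabolic syndrome. The protocol gives neither the number affected nor the direction or size of any bias, and none is asserted. The gap should be fixed because it reaches the primary objectives and is cheap to close.

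**What to change.** Add to the group definitions: *For research grouping only, current drug treatment for high blood pressure, as recorded at enrolment, counts as meeting criterion 2.* Repeat the Control–MS comparison without users of blood-pressure drugs as a sensitivity analysis. No change to any patient's treatment is implied.

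Two details need attention. The questionnaire must capture current use and the reason for it, since some of these drugs may be taken for other conditions. The protocol should also say whether the same rule applies when the five parameters are reassessed at Phase 2 visits, or only to the group assigned at enrolment.

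The cost is one sentence and one repeated comparison on data already collected, with two downsides:
- More candidates are needed to fill the Controls, as shown in the working; the number depends on a share the protocol does not give.
- Use of these drugs would then occur only in Partial and Full, where a drug effect could be mistaken for an MS effect. The repeat comparison addresses this, with smaller MS groups.

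Excluding users of blood-pressure drugs altogether would also settle the labels, but would remove them from Partial, Full and Phase 2.

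### Nothing in the Phase 1 eligibility or stool-collection rules restricts recent systemic antibiotic use, so the healthy reference and the group contrast can include stool altered by it

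*Protocol*

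**What the plan says.** Two of the six exclusion criteria in the protocol (Phase 1, Exclusion criteria) concern drugs. Item 3 reads "On long-term regular immunosuppressive therapy" and item 6 reads "Current medication for glucose or lipid control, such as metformin and statin". Antibiotics are mentioned nowhere in the protocol, and no drug has a washout or look-back period.

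The reference group is defined by metabolic status alone: "Controls (Non-Metabolic Syndrome): none of the five criteria". One stool sample is taken from each subject at enrolment. The questionnaire at that visit covers "diet, lifestyle, socioeconomic status, history of illnesses and medication use", without naming antibiotics, supplements or a recall period. The section on microbial data generation and analyses says that results will be correlated with the questionnaire answers. It says nothing about deferring, flagging or removing samples.

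Three objectives depend on these samples:
- Primary objective 1: "Generate a reference healthy gut microbiome database representative of the general adult population in Hong Kong".
- Primary objective 2: "Describe how the gut microbiomes of individuals with MS deviate from the healthy reference".
- Secondary objective 2: "Characterise changes in gut microbiome in response to medical treatment, supplementation with probiotics/prebiotics, changes to lifestyle and other interventions".

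**The concern.** The protocol treats drug intake as something the gut microbiome responds to, and it keeps users of glucose and lipid drugs out of Phase 1. Antibiotics act on bacteria by design. A completed short course nevertheless falls outside both drug exclusions, because one covers long-term therapy and the other covers current metabolic drugs.

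Three uses of the enrolment stool are exposed:
- **Healthy reference.** It can contain samples that reflect a recent course of treatment.
- **Group contrast.** Exposure adds variance in every group. It adds bias if exposure differs between groups, which is possible because subjects come both from public invitation and from clinic referral.
- **Phase 2.** Its subjects come from Phase 1 and no separate baseline stool is described, so the enrolment stool is presumably the starting sample. Recovery after antibiotics could then be read as a response to a later intervention.

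**Working it through.** **Inputs from the protocol (Phase 1, Sample size).** 731 subjects, 80% power, a 1% difference in diversity, 95% confidence, and a planned 500 per group. No SD, diversity index or sidedness is given, nor whether 731 is a total or a per-group number. The 731 therefore cannot be reproduced. It can only be solved backwards for the SD it implies.

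**Implied SD.** With n per group, SD = 1% / [(z for alpha + z for power) × √(2/n)], as a percentage of mean diversity.

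| Reading of 731 | Two-sided | One-sided |
|---|---|---|
| Total, 1:1 (n = 365.5) | 4.83 | 5.44 |
| Per group (n = 731) | 6.82 | 7.69 |

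For the first cell: (1.960 + 0.842) × √(2/365.5) = 0.2072, and 1/0.2072 = 4.83. The two two-sided values are used below.

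**Assumed inputs.** The documents give neither the share of subjects recently exposed nor the fall in diversity among them. Both are assumptions.

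**Bias from unequal exposure.** If a share p of a group is exposed and diversity is lower by a fraction e in those subjects, the group mean falls by e × p. The spurious difference between two groups is e × (difference in p), whatever the SD. The false-positive rate when there is no true difference, at 500 v 500 and two-sided 0.05, uses a standard error of SD × √(2/500).

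| Exposure difference | Fall in exposed | Spurious difference | False-positive rate, SD 4.83 | SD 6.82 |
|---|---|---|---|---|
| 0 points | any | 0 | 5% | 5% |
| 2 points | 10% | 0.2% | 10% | 8% |
| 5 points | 5% | 0.25% | 13% | 9% |
| 5 points | 10% | 0.5% | 37% | 21% |
| 5 points | 20% | 1.0% | 91% | 64% |

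In the fourth row, 0.05 × 10% = 0.5%, half the planned effect. In the last, 0.05 × 20% = 1.0%, the whole of it.

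**Variance from equal exposure.** The SD becomes √(SD² + e² × p × (1 − p)). With p = 0.10 and e = 10%, e² × p × (1 − p) = 100 × 0.09 = 9. The SD rises from 4.83 to about 5.7, and power at 500 v 500 for a 1% difference falls from 91% to about 79%. From an SD of 6.82 it rises to 7.45, and power falls from 64% to 56%. Over 5 to 20% exposed and a 5 to 20% fall, power ranges from 89% down to 40% (SD 4.83) and from 63% down to 32% (SD 6.82).

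**The case against.** **Exposure is not documented.** A reader might infer that the reference and the contrast do contain altered samples, or that the contrast is biased. The protocol supports neither. It gives no exposure rate and no sign that exposure differs between groups. It supports only that such samples can enter.

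**The power figures are fragile.** A reader might take the fall in power as a failure of the design. It rests on assumed exposure and a back-solved SD. The 731 came from published cohort data. If that cohort included exposed people, their variance is already counted. The protocol also raised its numbers because of high variability, and in the middle scenario power at 500 v 500 stays close to the nominal 80% on the 4.83 reading. This objection stands, so the power loss is not the main argument.

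**Medication use is recorded.** Enrolment covers "history of illnesses and medication use", and handling in the analysis may be left to a statistical analysis plan that is not at hand. This stands in part, since adjustment or a sensitivity analysis belongs there. But such a plan cannot re-time stool already collected, nor recover a date of last use that was never asked.

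**Probiotics.** It is tempting to extend the restriction to probiotic and prebiotic users among Controls. The documents do not support that. Habitual users belong to the general adult population that primary objective 1 aims to represent. Removing them from Controls alone would also make exposure unequal by design in primary objective 2. Nothing in the protocol suggests that supplements lower diversity by the amounts assumed above.

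**Conclusion.** The point holds as a gap in the Phase 1 eligibility and sampling rules: recent systemic antibiotic use is unrestricted, and its timing is not explicitly captured. Both primary objectives are exposed to it directly. Phase 2 is exposed by inference, because no passage designates its baseline sample.

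The size is unknown. Equal exposure across groups adds variance without creating a spurious difference. The 0.5 to 1.0% illustration rests entirely on an assumed 5-point exposure difference and an assumed 10 to 20% fall in diversity, and with smaller values the effect is minor. The gap still matters because the planned difference is only 1%, and because it cannot be fully repaired once the stool is collected.

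**What to change.** 1. Add one sample-timing rule, identical for the Full, Partial and Control groups: defer the enrolment stool until a fixed look-back, chosen and stated by the investigators, has passed since the last systemic antibiotic. The subject is kept and only the specimen waits. Patient care is unaffected.
2. Add to the enrolment questionnaire the date of last systemic antibiotic use and current probiotic or prebiotic use.
3. Leave samples that do not meet the rule out of the reference and the primary contrast.
4. Do not exclude probiotic or prebiotic users from Controls only. Record use in all three groups, then adjust for it or run a sensitivity analysis. Supplements begun during Phase 2 remain an exposure of interest.

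The cost is a short amendment, two questionnaire items, some postponed stool collections and slightly slower recruitment.

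### Does the forecast of six to nine samples per subject conflict with visits every 3 to 6 months over 36 months?

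*Protocol*

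**What the plan says.** All the relevant text stands in the Protocol, Phase 2: Longitudinal observational study, under the list of what happens at follow-up visits.

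- Visit timing: subjects in the full and partial groups "will be re-examined at regular intervals according to the current practice of the clinic which depends on the need for drug treatment". The usual intervals are then described: "Patients started on new medication are usually followed-up at 4-6 weeks, those on regular medication at 3-6 months".
- Duration: "For the purpose of this study, each subject will be followed up to 36 months".
- Assessments: "The 5 parameters for metabolic syndrome will be reassessed at each follow-up visit".
- Specimens: "10 ml of fasting blood will be collected for glucose, triglycerides, cholesterol, and lipid measurements", and "A stool sample will be collected for studying changes in the gut microbiome". A urine sample is listed as well. No subset of visits is named for any of the three.
- Yield: subject to the individual's visit frequency, "each subject will be providing a total of six to nine blood, urine and stool samples over the 36-month duration of this study".

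The list gives no maximum number of samples and no rule for leaving a visit unsampled.

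**The concern.** The yield sentence ties the count to visit frequency, and the same list gives that frequency for treated subjects, so the count can be checked by division. One end passes and the other does not.

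For blood the mismatch looks sharper. The five criteria are to be reassessed at every follow-up visit. Three of them (triglycerides, HDL cholesterol and fasting sugar, in the Phase 1 study population criteria) need a blood sample. A subject seen every three months throughout would then give twelve blood samples, while the yield sentence speaks of nine at most.

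If nine were a limit, samples ten to twelve would be in doubt for such subjects, and the amount of blood drawn would be understated.

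**Working it through.** **Inputs**, all from the Phase 2 follow-up list: duration T = 36 months; usual interval d = 3 to 6 months on regular medication; an early visit at 4 to 6 weeks after new medication; 10 ml of fasting blood per sampled visit; stated yield 6 to 9.

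**Formula:** follow-up visits = T/d, with one sample set per visit.

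1. Lower end: 36/6 = 6. This reproduces the stated six.
2. Upper end: 36/3 = 12. This does not reproduce the stated nine; the difference is 12 − 9 = 3.
3. Interval implied by nine: 36/9 = 4 months, inside the 3 to 6 month range.
4. A schedule that changes over time can also give nine, for example 3-monthly for 18 months and then 6-monthly: 18/3 + 18/6 = 6 + 3 = 9.
5. Ten visits need an average interval of 36/10 = 3.6 months. At average intervals of 4 months or longer nothing exceeds the stated range.
6. Early visits: 4 to 6 weeks is about 0.9 to 1.4 months, which leaves 34.6 to 35.1 months. If the 3-month interval restarts from there, the count is 1 + 11 = 12, unchanged. Two such restarts give 2 + 11 = 13.
7. Counting enrolment would give 7 to 13 for stool and blood. That reading fits the sentence poorly, because the sentence includes urine and no urine is listed at enrolment.
8. Blood at follow-up: 9 × 10 = 90 ml; 12 × 10 = 120 ml; difference 30 ml over 36 months.

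**What depends on the count.** The sample size section works in subjects (731 for the power statement, about 1000 for Phase 2), not in samples per subject. The group definitions use the five criteria. The described analysis correlates microbiome profiles with questionnaire and clinical data. None of these uses six to nine as an input.

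**The case for a change.** The strongest case for a change is that the sentence gives a total for each subject over the whole 36 months, and that blood is needed at every visit. On that reading, a subject seen 3-monthly has twelve samples under one statement and at most nine under another. The 4-month average and the mixed schedule that would yield nine are nowhere stated.

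Part of this stands. The stated range is narrower than the stated intervals allow, and nothing in the text explains the nine. The two statements do not fit together for a subject seen at the shortest usual interval throughout.

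The rest does not carry. The intervals describe what the clinic usually does, and follow-up has an upper limit, not a fixed length. An observational study that leaves patient management alone would not be expected to state a schedule for reaching nine. Varying intervals are likely: people already on glucose or lipid medication are excluded at entry, visit timing depends on the need for drug treatment, and no interval is given for untreated subjects. The yield sentence contains no wording of a maximum. Staff who follow the list take samples at the follow-up visits, and nothing tells them to stop at nine. The protocol contains no sample budget or cumulative blood volume that the figure would make wrong.

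**Conclusion.** The arithmetic of the concern is right: 3 to 6 month visits over 36 months allow 6 to 12 sample sets, against a stated six to nine. It remains a loose forecast and calls for no change to the plan.

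At a constant 3-month interval for the full 36 months the excess is three sample sets and 30 ml of blood per subject; two early visits that each restart the interval would add one more set. How many subjects this applies to is unknown, and it may be few or none.

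Sampling at follow-up visits as listed gives sound data whether a subject contributes six sets or twelve. Because visits follow clinic practice, the number of repeated measures will differ between subjects in any case, and the analysis has to allow for that. Wording the range as approximate, or widening it, would make the two statements agree but would alter no result.

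This rests on reading six to nine as an expectation and not as a ceiling. The text supports that reading, since it makes the number depend on visit frequency and sets no limit.
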